## 1.1. Schedule of Activities

**Table 1 RVT-901-3004 Schedule of Activities**

Study Period:	Treatment						Safety Follow-up/ Unscheduled	
Visit Number:	Visit #6	Visit #7	Visit #8	Visit #9	Visit #10	Visit #11	UNS #	Visit #12
Visit Name:	Week 12	Week 16	Week 24	Week 36	Week 44	Week 52 or Early WD	Unsch- eduled 	Follow- up 
Study Day:	85	113	169	253	308	365		393 or WD + 28
Permitted Visit Window:	± 3 Days	± 3 Days	± 3 Days	± 3 Days	± 3 Days	± 3 Days		± 3 Days
Informed Consent	X 							
Inclusion/Exclusion Criteria Eligibility Review	X 							
Electronic Diary (eDiary)  :								
eDiary Device								
Device Function Check 	X 	X	X	X	X	X	X	
Device Re-Training 	X 	X	X	X	X		X	
Collect eDiary Device						X		
Patient Voiding Diary:								
Voiding Diary Re-Training 	X 	X	X		X	X	X	
Patient Completes Voiding Diary 	X*	X	X		X	X		
Urine Volume Diary:								
Voided Volume Diary Re-Training 	X 	X	X		X	X	X	
Patient Completes Voided Volume Diary 	X*	X	X		X	X		
Diary and Visit Reminders								
Phone Calls/ Optional SMS reminders 	X*	X	X		X	X		
Patient Reported Outcomes (PROs)  :								
Global Impression Items (PGI-Severity, PGI-Control, PGI-Frequency, PGI-Leakage, and PGI-Change)	X*		X			X		
Overactive Bladder Questionnaire (OAB-q LF)	X*		X			X		
Work Productivity and Activity Impairment Questionnaire-Urinary Symptoms (WPAI-US)	X*		X			X		
EQ-5D	X*		X			X		
Post-Void Residual (PVR) Volume 	X*		X			X		
Physical Exam 	X 						X	X
EKG 	X 						X	
Vital Signs 	X*	X	X	X	X	X	X	X

Study Period:	Treatment						Safety Follow-up/ Unscheduled	
Visit Number:	Visit #6	Visit #7	Visit #8	Visit #9	Visit #10	Visit #11	UNS #	Visit #12
Visit Name:	Week 12	Week 16	Week 24	Week 36	Week 44	Week 52 or Early WD	Unsch- eduled 	Follow- up 
Study Day:	85	113	169	253	308	365		393 or WD + 28
Permitted Visit Window:	± 3 Days	± 3 Days	± 3 Days	± 3 Days	± 3 Days	± 3 Days		± 3 Days
Adverse Event Review 	←=====→							
Serious Adverse Events 	←=====→							
Concomitant Medication Review 	←=====→							
Clinical Laboratory Assessments:								
Chemistry	X*	X	X			X	X	X
Hematology	X*	X	X			X	X	X
Urine Dipstick 	X*	X	X			X	X	X
Urine Pregnancy β-hCG (women) 	X*	X	X	X	X	X	X	X
IxRS Randomization to Study Treatment	X 							
Dispense Study Treatment 	X 	X	X	X	X		X	
Study Treatment Return/Accountability Review 	X*	X	X	X	X	X		
Administer Witnessed Dose of Study Treatment 	X 							

Abbreviations: IxRS, interactive voice or web response system; WD, withdrawal; β-hCG, β-human chorionic gonadotropin

**Table Footnotes:**

**Week 12**

1. Patients continuing from the RVT-901-3003 study at Week 12 require additional study procedures for the RVT-901-3004 extension study.

\* Activities collected at Week 12 Visit in RVT-901-3003.

**Electronic Diary (eDiary)**

2. The Electronic Diary (eDiary) for this study includes both the Patient Voiding Diary and the Urine Volume Diary, and will be implemented via an eDiary device (provisioned smartphone). A paper diary will be provided to all patients to be used as a back-up when necessary. If a back-up paper diary is used, it should be collected at the next visit.
3. The site will update the Subject Status Screen on the eDiary to move the patient to the RVT-901-3004 extension study.

**eDiary Device**

4. At each visit during the Treatment Period, site personnel will confirm that the eDiary Device is functioning properly.
5. Specific re-training on device operation will be provided to the patient at each visit.

**Patient Voiding Diary and Urine Volume Diary**

6. Specific re-training on completion of the Voiding Diary and Voided Volume Diary will be provided to the patient at each visit.
7. The Voiding Diary should be completed by the patient on all of the 7 Diary Days prior to the Week 16, 24, 44, and 52 Visits. Patient will receive an alert and/or phone call reminder to complete the diary.
8. The Voided Volume collection and Voided Volume Diary completion should be performed by the patient on one (1) of the 7 Diary Days prior to the Weeks 16, 24, 44, and 52 Visits.

**Diary and Visit Reminders**

9. Patient will receive phone call reminders from the site to complete the Diary on approximately the first day and third day of each diary collection period (or next business day). Patient may consent to additional SMS Text reminders (where available).

**Patient Reported Outcomes (PROs)**

10. Vital signs, followed by PRO Questionnaires, will be the first procedure performed at visits that include PRO administration. Questionnaires will be administered on paper at the site in the order listed in the Schedule of Activities.

**Post Void Residual Volume**

11. All efforts will be made to ensure the same device and operator are used for all PVR volume measurements for individual patients (in study RVT-901-3003 and RVT-901-3004).

**Physical/ECG/Vitals**

12. A Complete Physical Exam will be performed at the Follow-up Visit.
13. A single 12-lead ECG will be obtained at Week 12.
14. Vital Signs includes Blood Pressure (average of three measurements taken 1-2 minutes apart after sitting for 5 min), Heart Rate, Temperature, Respiration Rate, and Weight.

**Adverse Events**

15. Adverse Events will be collected from the time a patient takes the first dose of Study Treatment in the RVT-901-3004 study until the Follow-up Visit is completed.

16. Serious Adverse Events will be collected from the time a patient takes the first dose of Study treatment in the RVT-901-3004 study until the Follow-up Visit is completed.

**Concomitant Medications**

17. Concomitant medications from RVT-901-3003 will be reviewed and confirmed to be stable. Concomitant medications will be recorded at each study visit and at any Unscheduled Visits.

**Labs**

18. At Weeks 36 and 44, the Urine Dipstick will only be performed if clinically indicated (e.g., symptoms of urinary retention or urinary tract infection). Urinalysis will be performed only if the urine dipstick tests positive for the presence of leukocytes, nitrites, or blood cells, and will be performed by the central lab.
19. Urine beta-human chorionic gonadotropin ( $\beta$ -hCG) will be tested for women of childbearing potential only.

**Dosing/Drug**

20. Dosing will occur every day from the Witnessed Dose on the day of the Week 12 Visit through the day before the Week 52 Visit.
21. Study Treatment bottles should be returned by the patient at each visit. Clinic staff will perform accountability and review any discrepancies with the patient during the visit.
22. All patients will take their dose of Study Treatment on the day of the Week 12 Visit at the site as a witnessed dose. The date and time of Study Treatment dosing will be recorded.

**Follow-up/Unscheduled**

23. Unscheduled Visits and the specific procedures performed at these visits will be determined by the Investigator, as clinically indicated. The procedures indicated in the Schedule of Activities will be performed at these visits, as clinically indicated, based on the purpose of the visit (e.g., follow-up for an adverse event or abnormal laboratory test, dispense study treatment medication). The reason for the visit will be captured in the source documents.
24. For patients who complete the study or who Withdraw from the study early for any reason, a Follow-up Visit should be performed approximately 28 days after the last dose of Study Treatment (on Study Day 393 or approximately 28 days after a patient's Withdrawal from the study). When a patient withdraws from the study prior to study completion, all applicable activities scheduled for the Week 52 Visit should be performed at the time of withdrawal.

## 2. INTRODUCTION

### 2.1. Indication

Vibegron (RVT-901) is currently in development to reduce urge urinary incontinence, urgency, and urinary frequency in patients with overactive bladder (OAB).

### 2.2. Background

OAB affects approximately 16% of the population in the US and EU. Prevalence increases with age, affecting approximately 1/3 of people 75 years and older [Stewart, 2003; Milsom, 2001]. The International Continence Society (ICS) defines OAB as urgency, with or without urge incontinence, usually associated with frequency and nocturia [Abrams, 2002]. Urgency is defined as a sudden compelling desire to void which is difficult to defer. Urge urinary incontinence (UUI) is the involuntary loss of urine accompanied by urgency (referred to as OAB Wet) and is present in approximately one-third of patients with OAB [Stewart, 2003; Milsom, 2001]. In the absence of incontinence, OAB is referred to as OAB Dry. UUI is distinguished from stress urinary incontinence, which is the involuntary loss of urine on effort or physical exertion (e.g., sporting activities), or on sneezing or coughing. When both components are present, the classification is mixed urinary incontinence and the Investigator will make a determination of either urgency or stress specified as the predominant component.

Currently, the predominant class of drugs used to treat OAB is antimuscarinics. The clinical use of antimuscarinics is limited by modest efficacy and poor tolerability due to mechanism-based side effects including dry mouth, constipation, and the potential for CNS adverse effects (e.g., cognitive impairment). High discontinuation rates have been observed for both tolterodine and oxybutynin, two commonly prescribed antimuscarinics, in both clinical trials and marketed settings [D'Souza, 2008; Lawrence, 2000]. In a study evaluating the discontinuation rate of new prescriptions for tolterodine ER or oxybutynin, the mean time to discontinuation was 45 to 60 days, and over 55% of patients never refilled their original prescription [Lawrence, 2000]. At six months, less than 1/3 of patients were still refilling their prescriptions. The lack of efficacy or inability to tolerate antimuscarinics leaves patients with few alternative treatment options. As such, there is a clear unmet medical need for better treatment options for patients with OAB. In addition, recent evidence from observational studies suggests that higher cumulative anticholinergic use is associated with an increased risk of dementia [Gray, 2015; Gray, 2016].

Beta-3 adrenergic receptor ( $\beta_3$ -AR) agonists demonstrated efficacy in alleviating symptoms of OAB [Chapple, 2009; Chapple, 2010; Chapple, 2012]. To date, one  $\beta_3$ -AR agonist, mirabegron (Astellas Pharma Global Development, Inc.), has received marketing approval in Japan and the United States for the treatment of OAB. Reductions in micturition frequency, urinary incontinence and urgency episodes, and increases in mean volume voided per micturition were observed with mirabegron [Chapple, 2009; Chapple, 2010; Chapple, 2012]. Cross-study comparisons of the clinical profiles of  $\beta_3$ -AR agonists with the antimuscarinic, DETROL® LA (tolterodine tartrate extended release, hereafter referred to as tolterodine ER), suggest that  $\beta_3$ -AR agonists possess similar efficacy for the treatment of OAB with an improved tolerability profile [Chapple, 2009; Van Kerrebroeck, 2001]. A recent publication demonstrated that patients prescribed mirabegron remained on treatment longer and showed greater adherence than those

[figure not shown]
[figure not shown]
prescribed traditional antimuscarinics, and mirabegron was associated with a favorable safety and tolerability profile [Chapple, 2017].

Vibegron is a potent, highly selective, orally available  $\beta_3$ -AR agonist demonstrating >9,000 fold selectivity for activation of  $\beta_3$ -AR over  $\beta_2$ -AR and  $\beta_1$ -AR in cell based in vitro assays. Beta-adrenergic receptors ( $\beta$ -AR) are prototypic G-protein coupled receptors expressed on the surface of cells and mediate intracellular signaling via coupling to G proteins and increasing levels of intracellular cyclic adenosine monophosphate (cAMP).  $\beta_3$ -ARs are widely distributed in humans and are the most prevalent  $\beta$ -AR subtype expressed on human detrusor smooth muscle [Takeda, 2000]. In isolated human bladder smooth muscle, activation of  $\beta_3$ -AR using subtype-selective agonists results in smooth muscle relaxation suggesting a role of  $\beta_3$ -AR agonists during the filling phase of the micturition cycle [Yamaguchi, 2002; Biers, 2006]. In rodent models of bladder overactivity,  $\beta_3$ -AR agonists relax bladder smooth muscle and suppress non-neurogenic and neurogenic detrusor over activity [Takeda, 2000; Woods, 2001; Takeda, 2002; Kaidoh, 2002]. In rhesus monkeys, dose-dependent increases in bladder capacity and decreases in micturition pressure were observed with vibegron. Bladder capacity was further increased by vibegron in combination with tolterodine or darifenacin.

### **2.3. Study Rationale**

The use of vibegron in a large Phase 2b study (Study 008) in patients with OAB has demonstrated encouraging safety, tolerability, and efficacy results. Furthermore, Phase 3 data in Japan (Studies 301 and 302) have demonstrated that vibegron is a safe, well tolerated, and effective therapy for OAB patients. Given there are still OAB patients that do not reach their treatment goals with currently approved therapies, there remains an unmet need for new OAB therapies with a favorable safety, tolerability, and efficacy profile. This study is designed to evaluate the long-term safety, tolerability, and efficacy of vibegron 75 mg administered once daily in patients with OAB.

### 3. OBJECTIVES AND ENDPOINTS

Objectives	Endpoints
Primary Safety	

 
To evaluate the safety and tolerability of vibegron for up to 52 weeks in patients with symptoms of overactive bladder (OAB) who previously completed treatment in study RVT-901-3003
 
	
 
Incidence of any treatment-emergent adverse event by system organ class and preferred term
 

Secondary and Exploratory	

 
To evaluate the efficacy of vibegron in patients with symptoms of OAB
 
 	
Secondary Endpoints:
 
 
Change from baseline (CFB) at Week 52 in average number of micturitions per 24 hours in all OAB patients
 
CFB at Week 52 in average number of urge urinary incontinence (UI) episodes per 24 hours in OAB Wet patients
 
CFB at Week 52 in average number of urgency episodes (need to urinate immediately) over 24 hours in all OAB patients
 
CFB at Week 52 in average number of total urinary incontinence episodes over 24 hours in OAB Wet patients
 
 
Exploratory Endpoints:
 

Objectives	Endpoints

## 4. INVESTIGATIONAL PLAN

### 4.1. Overall Study Design

This is an international Phase 3, randomized, double-blind, active (tolterodine)-controlled, 40-week extension study to evaluate the safety, tolerability, and efficacy of vibegron 75 mg administered once daily in patients with OAB.

This study is an extension for patients who have completed the Phase 3, double-blind, randomized, 12-week study RVT-901-3003, which evaluated the efficacy, safety, and tolerability of vibegron 75 mg administered once daily in patients with OAB. Approximately 500 men and women with overactive bladder who completed 12 weeks in study RVT-901-3003 will be permitted to enroll in this extension study.

During the study, all patients who had been randomized in RVT-901-3003 to receive either vibegron 75 mg or tolterodine ER 4 mg will continue their same treatment once daily in a blinded fashion for 40 weeks during the extension; patients who had been randomized to the placebo group in RVT-901-3003 will be randomized 1:1 to receive blinded study treatment of vibegron 75 mg or tolterodine ER 4 mg once daily for 40 weeks during the extension. Thus, through participation in both the RVT-901-3003 study and the RVT-901-3004 (extension) study, patients originally randomized to vibegron or tolterodine will receive 52 weeks total of vibegron or tolterodine treatment and patients originally randomized to placebo will receive 40 weeks total of vibegron or tolterodine treatment.

[figure not shown]
Study visits will be named to reflect continuation from the RVT-901-3003 study, with the first study visit of this extension study occurring at Week 12. Following enrollment in this extension study, patients will return to the clinic for visits at Week 16, Week 24, Week 36, Week 44 and Week 52 (all relative to Day 1 of RVT-901-3003).

The study consists of a randomized double-blind Treatment Period (40 weeks) and a Safety Follow-up Period (4 weeks). All patients will have a Safety Follow-up Visit approximately 28 days after the patient's last dose of study treatment (i.e., at Week 56 for patients who complete the Week 52 Visit, or approximately 4 weeks after withdrawal for patients who discontinue the study early). Additionally, unscheduled follow-up visit(s) may be arranged for patients with study-related safety concerns as needed.

Specific procedures to be performed during the study, as well as their prescribed times and associated visit windows, are outlined in the Schedule of Activities ([Table 1](#)). Details of study procedures are provided in [Section 7](#).

A schematic of the study design is shown as [Figure 1](#).

**Figure 1 RVT-901-3004 Study Schematic**

\*The Follow-up visit occurs at Day 393 for subjects who complete the Week 52 visit or at 28 days after withdrawal (WD) for subjects who withdraw early from the study.

## **4.2. Treatment Arms and Duration**

Refer to Section 6 for full details of Study Treatments. Patients will receive one of the following blinded treatments during this extension study:

- Vibegron 75 mg tablet + placebo capsule to match tolterodine ER 4 mg capsule; both oral and administered once daily
- Tolterodine ER 4 mg capsule + placebo tablet to match vibegron 75 mg tablet; both oral and administered once daily

Dosing will begin at the Week 12 Visit (i.e., the baseline visit of the extension study), and once daily dosing of the Study Treatment will continue through Study Day 364, the day before the Week 52 Visit.

## **4.3. Number of Participants**

Approximately 500 patients will be enrolled.

## **4.4. Definition of Study Completion by a Patient**

A patient is considered to have completed the study if she/he completes the Week 52 Visit.

## **4.5. End of Study Definition**

End of study is defined as the date when the last patient has either completed the study (see Section 4.4 for definition of completion), has discontinued from the study, or is lost to follow-up (i.e., the patient is unable to be contacted by the Investigator).

## **5. STUDY POPULATION**

### **5.1. Eligibility Criteria**

To be eligible for participation in this study, a patient must have completed participation in study RVT-901-3003, and continue to meet all the Inclusion Criteria, and none of the Exclusion Criteria.

#### **5.1.1. Inclusion Criteria**

1. Has completed participation in study RVT-901-3003.
2. Willing and able to provide written informed consent.
3. For females of reproductive potential: Agrees to remain abstinent or use (or have their male partner use) an acceptable method of birth control (as defined in Section 5.2.1) each time the patient has intercourse until the Follow-up Visit.
4. For females of reproductive potential: Agrees not to donate ova (eggs) until at least 1 month after the last dose of Study Treatment.
5. Has demonstrated  $\geq 80\%$  compliance with self-administration of Study Treatment in study RVT-901-3003.
6. Has completed a minimum of 4 Complete Diary Days for study RVT-901-3003 Week 12.
7. Is ambulatory and in good general physical and mental health as determined by the Investigator.
8. In the opinion of the Investigator, is able and willing to comply with the requirements of the protocol, including completing questionnaires, the Voiding Diary, and Voided Volume Diary (will require ability to collect, measure, and record voided volume by herself/himself using a graduated urine collection and measurement container [provided by the Sponsor, if needed]).

#### **5.1.2. Exclusion Criteria**

1. Was unable to complete participation in study RVT-901-3003 for any reason.
2. Has a change in history or current evidence of any clinically significant condition, therapy, lab abnormality, or other circumstance that might, in the opinion of the Investigator, confound the results of the study, interfere with the patient's ability to comply with study procedures, or make participation in the study not in the patient's best interest. Includes any serious or unstable, clinically relevant change in gastrointestinal, renal, hepatic, cardiovascular, lymphatic, or psychiatric, or other medical disorder during the RVT-901-3003 study
3. Has coronary or neurovascular interventions planned during the duration of the study.
4. Has uncontrolled hyperglycemia (defined as fasting blood glucose  $>150$  mg/dL or 8.33 mmol/L and/or non-fasting blood glucose  $>200$  mg/dL or 11.1 mmol/L) based on most recent available lab results in study RVT-901-3003 or, if in the opinion of the Investigator, is uncontrolled.

5. Has uncontrolled hypertension (systolic blood pressure of  $\geq 180$  mm Hg and/or diastolic blood pressure of  $\geq 100$  mm Hg) or has a resting heart rate (by pulse)  $> 100$  beats per minute.
  - a. Patients who have systolic blood pressures  $\geq 160$  mm Hg or  $< 180$  mm Hg are excluded, unless deemed by the Investigator and/or Medical Monitor as safe to proceed in this study and able to complete the study per protocol; these patients must be on stable hypertension medication for at least 90 days.
  - b. All patients with signs and symptoms of uncontrolled hypertension, regardless of blood pressure measurement, are excluded from the study. These include, but are not limited to neurological symptoms or findings, hematuria, proteinuria, retinopathy, unstable angina, acute heart failure.
6. Has clinically significant ECG abnormality which, in the opinion of the Investigator, exposes the patient to risk by participating in the study
7. Has alanine aminotransferase or aspartate aminotransferase  $> 2.0$  times the upper limit of normal (ULN), or bilirubin (total bilirubin)  $> 1.5 \times$  ULN (or  $> 2.0 \times$  ULN if secondary to Gilbert syndrome or pattern consistent with Gilbert syndrome) based on most recent available lab results in study RVT-901-3003.
8. Has an estimated glomerular filtration rate (eGFR)  $< 30$  mL/min/1.73 m^2 based on most recent available lab results in study RVT-901-3003.
9. Use of any prohibited medications as detailed in Section 7.7.3.
10. Plans to initiate or change the dosing of any medications listed in Section 7.7.5 during the study that in the opinion of the investigator is assessed to be clinically significant.
11. Has an allergy, intolerance, or a history of a significant clinical or laboratory adverse experience associated with any of the active or inactive components of the vibegron formulation or tolterodine formulation.
12. Is currently participating or has participated in a study with an investigational compound or device within 28 days of signing informed consent, not including participation in study RVT-901-3003.
13. Has a history of significant drug or alcohol abuse/dependence within a year of informed consent, as assessed by the investigator.
14. Has a varying sleep schedule anticipated during times when the voiding diaries are to be completed.

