## **7.6. Inclusion/Exclusion Criteria**

Prior to randomization in RVT-901-3004, all inclusion and exclusion criteria will be reviewed by the Investigator or qualified designee to ensure that the patient qualifies for the study.

All inclusion criteria must be met and none of the exclusion criteria may apply. No eligibility waivers will be granted.

Patients found ineligible during review of inclusion/exclusion will not proceed through the randomization process.

Compliance with self-administration of Study Treatment in study RVT-901-3003 will be calculated based on the tablet/capsule counts recorded in the IxRS of the Run-In and Treatment phase in study RVT-901-3003 (Visits #2 through Visit # 6).

Laboratory results from the Week 4 Visit of RVT-901-3003 study will be used as a basis to confirm eligibility for glucose, AST, ALT, and eGFR. Urine pregnancy test, Urine dipstick results, ECG and average blood pressure measure will be confirmed prior to randomization. Concomitant medications will be reviewed at to ensure required stability.

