### **7.16. Vital Signs**

Vital signs including blood pressure, heart rate, respiration rate, and temperature (oral or tympanic) will be obtained at all visits after patients have rested quietly in a sitting position for 5 minutes.

Three blood pressure measurements will be taken in a sitting position and performed on the same arm and by the same site staff, if possible, for each patient throughout the study. The following instructions should be followed:

- Sitting systolic and diastolic blood pressures will be determined by averaging 3 replicate measurements obtained 1 to 2 minutes apart. The average of the 3 replicate blood pressure measurements will be used for eligibility and safety assessments (not an individual value).

The same method for assessing temperature should be used at all visits for a particular patient.

Body weight will be measured with patients in street clothing with jacket/coat and shoes removed.

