### 8.6. Adverse Events of Clinical Interest

Selected non-serious and serious adverse events will be reported as Adverse Events of Clinical Interest (AECI) and must be reported **within 24 hours of the study site personnel’s knowledge of the event** as an AECI by marking the appropriate box on the AE eCRF form and assigning the most appropriate category. Additional information requested should be provided as directed in the eCRF Completion Guidelines (eCCGs).

AECIs that also meet the definition of a serious adverse event must be reported as a serious adverse event, as described in Section 8.3.2.

Adverse Events of Clinical Interest for this study include:

- Potential Major Adverse Cardiac and Cerebrovascular Events (MACCE), which will be adjudicated by an independent external expert clinical adjudication committee (CAC) into the following categories according to the definitions in the CAC Charter:
  - Death or any event with fatal outcome
  - Myocardial infarction / Heart Attack
  - Cerebrovascular Accident / Stroke
  - Hospitalization for Unstable Angina / Chest Pain
  - Hospitalization for Heart Failure
  - Coronary revascularization / Angioplasty / Stent
- Hypertension:

An adverse event of hypertension should be reported and will be an AECl as follows:

  - For patients without hypertension (average SBP <140 mmHg, DBP <90 mmHg) at baseline, at two consecutive visits, the average of three systolic blood pressure (SBP)  $\geq$ 140 mmHg or diastolic blood pressure (DBP)  $\geq$ 90 mmHg (or both); at 2 consecutive visits in patients who were not hypertensive at baseline; or,
  - For patients with hypertension at baseline, an increase compared to baseline at 2 consecutive visits in the average of three SBP by  $\geq$ 20 mmHg OR DBP by  $\geq$ 10 mmHg;
  - Initiation of, or increase in dose of, medication for treatment of hypertension in any patient.
- Adverse events consistent with orthostatic hypotension as confirmed by orthostatic vital signs.
- Adverse events suggestive of cystitis or urinary tract infection.
- Elevated AST or ALT lab value requiring that study drug be temporarily withheld or permanently discontinued (see Section 8.6.1 and Section 8.6.2).

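### Exclusion 5a joins its two systolic limits with *or*, so as written it covers every systolic pressure instead of the band from 160 to below 180 mm Hg

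*Protocol*

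**What the plan says.** Exclusion 5 in protocol section 5.1.2 opens with an outright bar: "Has uncontrolled hypertension (systolic blood pressure of" 180 mm Hg or more, a diastolic pressure of 100 mm Hg or more, or a resting heart rate above 100 beats per minute.

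Sub-item 5a then deals with patients whose systolic pressure is at least 160 "mm Hg or $< 180$ mm Hg are excluded, unless deemed by the Investigator and/or Medical Monitor as safe to proceed" and able to complete the study. It closes with a further condition: "these patients must be on stable hypertension medication for at least 90 days". The synopsis gives 5a with the same *or*. No other section states the rule as a band.

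Three sections make the criterion binding:

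- Section 5.1 requires that patients "continue to meet all the Inclusion Criteria, and none of the Exclusion Criteria".
- Section 7.6 says "All inclusion criteria must be met and none of the exclusion criteria may apply. No eligibility waivers will be granted", and that "ECG and average blood pressure measure will be confirmed prior to randomization".
- Section 7.16 fixes the value to be used: "The average of the 3 replicate blood pressure measurements will be used for eligibility and safety assessments (not an individual value").

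**The concern.** Two limits that should enclose a band have been joined so that they cover the whole scale. A criterion that every patient meets separates no one. The clause that follows then does all the work, because anyone caught by 5a must be judged safe to proceed and must also have been on stable antihypertensive medication for at least 90 days. The first of these is a matter of judgment; the second is not.

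Taken at its word, 5a would therefore restrict the extension to patients treated for hypertension. That is a different population from the one described in the rest of the protocol. Because the criterion is an eligibility threshold and waivers are ruled out, a site that noticed the problem would have no formal route for departing from the wording.

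**Working it through.** There is no sample size, power or error rate to reproduce here. The check is a logical one, followed by a comparison of sections.

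**Inputs.** Limits in 5a: systolic at least 160, below 180, joined by *or* (section 5.1.2 and synopsis). Outright limit in exclusion 5: systolic at least 180 (section 5.1.2). Limit for no hypertension at baseline: average systolic below 140 and diastolic below 90 mmHg (section 8.6). The range of 60 to 260 mm Hg is an assumption used only for counting; the protocol gives no range and no blood pressure distribution.

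**Step 1: the condition as written.** Let x be the systolic pressure. If x is 160 or more, the first limit is met. If x is below 160, it is also below 180, so the second limit is met. No value of x escapes, whatever range is chosen.

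**Step 2: counts on the illustrative range.** Whole numbers from 60 to 260: 260 − 60 + 1 = 201.

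| Condition | Values covered | Count |
|---|---|---|
| x ≥ 160 *or* x < 180 (as written) | 60–260 | 201 of 201 |
| x ≥ 160 *and* x < 180 (as intended) | 160–179 | 20 of 201 |

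The text covers 201 − 20 = 181 values too many. They fall into two parts:

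- 60–159: 100 values that 5a should not touch at all. Of these, 80 (60–139) lie below the 140 mmHg systolic limit that section 8.6 uses for no hypertension.
- 180–260: 81 values that exclusion 5 already bars outright.

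Check: 100 + 81 = 181.

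**Step 3: the literal rule against the rest of the protocol.**

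- *Section 8.6* defines the hypertension event separately "For patients without hypertension (average SBP <140 mmHg, DBP <90 mmHg) at baseline". That rule presupposes that normotensive patients are enrolled. Under the literal 5a, such a patient enters only if already on at least 90 days of stable antihypertensive medication.
- *Section 7.7.5* asks for a stable blood pressure regimen from patients with a history of hypertension. Under the literal 5a, the demand for medication would extend to everyone.
- *Exclusion 5* bars 180 mm Hg and above without exception. The literal 5a covers the same values again, this time with an exception attached.

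**Step 4: the intended rule.** Replacing *or* with *and* gives a band that ends exactly where the outright bar of exclusion 5 begins. The 90-day medication clause then applies to patients with raised but not prohibitive pressure. All three mismatches disappear.

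**The case against.** The strongest reply is that this is a one-word slip that nobody would follow. Sub-item 5a sits under a heading about uncontrolled hypertension, directly below the limit of 180, and refers to antihypertensive medication. On the literal reading both of its numbers are idle, so a sensible reader supplies the band. Much of this stands: most sites would probably read it as intended, and nothing in the protocol shows that any site or the randomization system applied the literal text.

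Other parts of the reply also hold:

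- Exclusions are cumulative, so the exception in 5a cannot readmit a patient at 180 mm Hg or above. The overlap there is redundant and does not loosen the limit. Only values below 160 could be affected.
- 5a carries its own discretion through the judgment that a patient is safe to proceed, and the ban on waivers does not remove it. The literal exclusion of untreated normotensive patients rests on the 90-day clause alone.
- The integer counts depend on an assumed range and give each value equal weight. They illustrate the logic and do not measure how many patients are affected.
- The analyses are descriptive, with no formal comparison planned, and no endpoint or analysis set is shown to change.

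What does not follow is that the text can be left alone. The reader has to infer the right rule because the stated one is wrong, in the operative criterion and in its only other statement. Eligibility thresholds belong in the protocol and cannot be put right in an analysis plan.

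**Conclusion.** The concern holds. As written, exclusion 5a applies to every systolic pressure. Followed literally, its medication clause would shut out untreated normotensive patients whom sections 7.7.5 and 8.6 plainly expect. The error is certain, because it follows from the wording alone. It is unlikely to come from the PDF conversion, because the synopsis has the same *or*.

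The size in practice is probably small. The band from 160 to below 180 mm Hg is an inference from exclusion 5, section 7.7.5 and section 8.6, since the protocol nowhere states it, but the inference is a safe one. No number of wrongly excluded patients is claimed, and no bias or loss of precision is alleged. The remaining risk is that the wording passes unchanged into an eligibility checklist, where it would produce a wrong answer for anyone below 160 mm Hg who is not on antihypertensive treatment. It should be corrected.

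**What to change.** In section 5.1.2 and in the synopsis, change the opening of 5a to read: patients who have systolic blood pressure ≥160 mm Hg **and** <180 mm Hg are excluded, unless … Leave the rest of 5a, including the safety judgment and the 90-day medication clause, as it stands.

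The cost is one word in two places. No data, visit, procedure or analysis changes.
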